14.3. Analysis Populations

Safety Population:

All subjects who were administered any test article excluding subjects who drop out prior to administering any test article. At least one observation should be recorded.

Per-Protocol Population:

All subjects who have successfully completed all visits and did not substantially deviate from the protocol as determined by the trial cohort review committee prior to database hard lock (Per-Protocol Population). Justification of excluding subjects with protocol deviations in the Per-Protocol Population set will be documented in a memo to file.

Intent-to-Treat (ITT) Population:

All subjects regardless of actual treatment and subsequent withdrawal from study or deviation from protocol. At least one observation should be recorded.

14.4. Level of Statistical Significance

All planned analysis for this study will be conducted with an overall type I error rate of 5%.

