2.3. Hypotheses

The following primary hypothesis will be tested throughout this investigation.

Primary Hypothesis:

1. After 14 to 20 days of wear, the PRO CLUE vision scores for the Test lens will be non-inferior to the Control lens. A non-inferiority margin of 5 CLUE points will be used. This will be recorded by the subject using the CLUE Follow-up Questionnaire.

If the primary hypothesis is met, the following secondary hypotheses will be tested.

Secondary Hypotheses:

1. After 14 to 20 days of wear, the distance, binocular, high luminance, high contrast visual acuity score for the Test lens will be non-inferior to the Control lens. A non-inferiority margin of -0.05 logMAR will be used.
2. After 14 to 20 days of wear, the intermediate, binocular, high luminance, high contrast visual acuity score for the Test lens will be non-inferior to the Control lens. A non-inferiority margin of -0.05 logMAR will be used.
3. After 14 to 20 days of wear, the near, binocular, high luminance, high contrast visual acuity score for the Test lens will be non-inferior to the Control lens. A non-inferiority margin of -0.05 logMAR will be used.

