14.2. Sample Size Justification

Historical study [REDACTED] tested hyperopes in presbyopic population. The data from [REDACTED] was used to estimate the sample size of the study. The rationale is the Test lens in [REDACTED] has the same optical and mechanical designs, but a different curing method compared with both test article in this trial.

Using the POWER procedure in SAS 9.4, the table below shows the power to test the primary hypothesis with overall type I error 0.05 and 50 subjects.

Primary Hypothesis:	Criteria	True Difference (Test-Control)	Power
CLUE Vision	Test-Control>=-5	0	0.48
		2	0.72
		4	0.89

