14.5. Primary Analysis

Primary efficacy analysis:

Overall quality of vision scores will be analyzed using a linear mixed model adjusting for baseline values as fixed covariates. The model will include the experimental design factors: sequence of lens wear, period, lens type, time point and interaction between lens and time point as fixed effects. The covariance between residual errors from the same subject across lens wearing periods/time point will be selected based on the finite-sample corrected Akaike's Information Criterion.⁶ Covariance structures considered may include: Homogenous compound symmetry (CS) and Unstructured covariance structure (UN). The structure that returns the lowest Akaike Information Criteria Corrected (AICC) will be selected as the structure that best fit the data.

Comparisons between the Test lens and Control lens at 2-week follow-up will be carried out using 95% confidence intervals constructed of least-square means (LSM) differences (Test minus Control) from the linear mixed model. The non-inferiority of the Test lens relative to the Control will be concluded if the lower confidence limit of LSM difference is above the non-inferiority margin -5. The superiority will be established if the lower confidence limit is above 0.

In all models, the Kenward and Roger method⁷ will be used for the calculation of the denominator of degrees of freedom.

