14.6. Secondary Analysis

Secondary efficacy analysis:

Binocular, high luminance, high contrast visual performance on logMAR scale will be analyzed using a linear mixed model to test for the difference between the study lens systems. Each model will include the experimental design factors: sequence of lens wear, lens wearing period, lens type, distance and the interaction between lens type and distance as fixed effects. Other baseline characteristics known of importance such as age, gender, and/or add power will be included as fixed covariates when appropriate. Site and subject nested in site will be included as random effects when appropriate. The covariance between residual errors from the same subject at the same distance across lens wearing periods will be selected based on the finite-sample corrected Akaike's Information Criterion.⁶ Covariance structures considered may include: Homogenous compound symmetry (CS) and Unstructured covariance structure (UN). The structure that returns the lowest Akaike Information Criteria Corrected (AICC) will be selected as the structure that best fit the data.

Comparisons between the Test lens and Control lens will be carried out using 95% confidence intervals constructed of least-square means (LSM) differences (Test minus Control) from the linear mixed models. The non-inferiority of the Test lens relative to the Control will be concluded if the upper confidence limit of LSM difference is below the non-inferiority margin 0.05 logMAR. The superiority will be established if the upper confidence limit is below 0.

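### The overall 5% type I error promised in 14.4 is not guaranteed: past the CLUE gate, three acuity non-inferiority hypotheses are each judged on an unadjusted 95% interval with no rule linking them

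*Combined protocol and SAP*

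**What the plan says.** Section 14.4 sets one error rate for everything planned: "All planned analysis for this study will be conducted with an overall type I error rate of 5"%. It does not say whether this is one-sided or two-sided.

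Section 2.3 names CLUE vision as the single primary hypothesis and then sets a gate: "If the primary hypothesis is met, the following secondary hypotheses will be tested". Three numbered secondary hypotheses follow, one each for distance, intermediate and near acuity. The numbering is not described as a testing sequence.

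Section 14.6 fits a model with a lens-by-distance interaction and uses 95% intervals. Non-inferiority "will be concluded if the upper confidence limit of LSM difference is below the non-inferiority margin 0.05 logMAR". It adds: "The superiority will be established if the upper confidence limit is below 0". Section 14.5 has the matching rule for CLUE: "The superiority will be established if the lower confidence limit is above 0". It does not say where that claim stands relative to the acuity hypotheses.

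Section 14.2 gives "the power to test the primary hypothesis with overall type I error 0.05 and 50 subjects", with criterion "Test-Control>=-5" and power 0.48, 0.72 and 0.89 at true differences of 0, 2 and 4.

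**The concern.** A gate between families protects the secondary family only when the primary is likely to fail. Once CLUE non-inferiority is met, nothing in the text limits the error across the three distances. A Test lens that truly loses 0.05 logMAR at every distance has three separate chances of being called non-inferior at one of them. The study report would then carry an overall 5% assurance that the decision rules do not supply. Section 1 says the purpose is to find out whether the manufacturing difference affects on-eye performance, so a false statement about acuity at one distance bears on the question asked.

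**Working it through.** **Inputs.** From 14.6: one limit of a 95% interval per test, so one-sided 0.025, with margin 0.05 logMAR. (Section 2.3 prints this margin as -0.05; the two need reconciling, and 14.6 is used here.) From 2.3: three hypotheses and one gate. From 14.2: n = 50, margin -5 and the three powers. Not in the documents, so assumed: the correlations among the acuity tests, the SD of CLUE differences and the SD of acuity differences.

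**1. The 14.2 power table.** Section 14.2 shows no SD. Solving for the standard error (SE) of the CLUE difference at one-sided 0.05, power = Φ((5 + d)/SE - 1.645). SE = 3.13 gives 0.48, 0.72 and 0.89 at d = 0, 2, 4, matching all three entries. A t-based calculation matches with SE = 3.09. At one-sided 0.025 no single SD fits all three; the best fit is 0.452, 0.731 and 0.911. So the table appears to read the 0.05 as one-sided, and that reading is used for the comparison below.

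**2. Past the gate, all three acuities at the margin.** If the tests are independent, P(at least one false claim) = 1 - 0.975³ = 0.0731. The Bonferroni bound is 3 × 0.025 = 0.075. For equally correlated normal statistics:

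| Assumed correlation | P(at least one false claim) |
|---|---|
| 0 | 7.3% |
| 0.3 | 6.8% |
| 0.5 | 6.3% |
| 0.7 | 5.5% |
| 0.8 | 4.9% |

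**3. With the gate included.** The 14.5 rule uses the 95% interval, so the gate runs at one-sided 0.025. The pass probability comes from the noncentral t with 48 df and SE 3.13. Multiplying by 0.0731 treats CLUE and the acuities as independent.

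| True CLUE difference | P(gate passes) | P(false acuity claim) |
|---|---|---|
| 0 | 0.347 | 2.5% |
| +2 | 0.592 | 4.3% |
| +4 | 0.804 | 5.9% |
| +8 | 0.983 | 7.2% |

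SE 3.09 moves these by about 0.1 percentage point at most. Using the powers printed in 14.2 as the gate instead gives 0.48, 0.72 and 0.89 × 0.0731 = 3.5%, 5.3% and 6.5% at 0, +2 and +4.

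**4. Superiority.** An upper limit below 0 is also below 0.05, so at one distance the superiority claim is nested in the non-inferiority claim. Each distance contributes at most 2.5% whatever its true value, and the ceiling in step 2 is unchanged. A simulation with all three differences at 0 gives 7.3% for any false acuity superiority, the same figure as at the margin.

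Primary superiority can be false only at a true CLUE difference of 0 or below. At exactly 0, with independence, adding it gives 0.025 + (0.347 - 0.025) × 0.0731 = 4.9%.

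**5. Under a fixed sequence.** A false acuity non-inferiority claim requires rejecting the first true null in the order, so its probability is at most 2.5% one-sided. For equal lenses, power per test is Φ(0.05/SE - 1.96) with SE = SD/√50:

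- SD 0.10: SE = 0.01414, power 0.942; all three pass under independence with probability 0.942³ = 0.84.
- SD 0.06: SE = 0.00849, power above 0.999; all three pass with probability close to 1.

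These powers are conditional on passing the primary gate.

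**The case against.** Four points can be made for the plan.

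- *The 7% is a corner case.* It needs a gate almost certain to pass, all three acuities at the margin, and independent tests. The acuities come from the same subjects at the same visit, so positive correlation is likely, and at about 0.8 the figure is already below 5%. After the gate it is also below 5% at true CLUE differences of 0 and +2. The +8 case lies outside the 0 to 4 range that 14.2 considers. All of this stands. It makes 7.3% a ceiling, but it does not restore a guarantee, because the plan states no correlation and relies on none.
- *Superiority.* A reader might infer that the superiority rules add four more uncontrolled chances of error. The documents do not support that. Acuity superiority is nested on the same interval and adds nothing beyond the ceiling. Only the primary superiority claim lacks a stated place, and at equality the total with it included is 4.9%.
- *Other readings.* Section 14.2 uses the same phrase about overall error for a single test, so 14.4 may loosely mean the test level. Section 14.6 also speaks of the non-inferiority of the Test lens in the singular, which could mean that all three distances must pass; the error would then be at most 2.5%. Both readings are possible, but neither is written down, and 2.3 lists three separate hypotheses.
- *Stakes.* This is a Phase 2 trial, the secondaries are already gated, and the primary claim is untouched. That limits the seriousness and is a fair reason to keep the change small.

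**Conclusion.** The point holds in a limited form. The rules in 2.3 and 14.6 do not guarantee the overall 5% in 14.4. The false acuity claim rate reaches 7.3% at most past the gate under independence, and is lower with positive correlation or an uncertain gate. The gated figures rest on an SE of about 3.1 recovered from 14.2 and on independence between CLUE and acuity.

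The comparison with 5% takes 14.4 as one-sided, as the power table implies. If 14.4 means 5% two-sided, or 2.5% in each direction, the gap past the gate is larger.

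A reader might infer that the trial's actual error rate is 7%, or that the primary conclusion is compromised. The documents support neither: the first depends on unknown correlations and true differences, and the primary non-inferiority test is a single test ahead of the gate. The defect is a missing rule among the three distances, together with an unplaced primary superiority claim.

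**What to change.** In 2.3 and 14.6, state that the three acuity hypotheses are tested in the order already numbered (distance, intermediate, near), each on the existing 95% interval, and that confirmatory claims stop at the first failure. Label the superiority statements in 14.5 and 14.6 descriptive, or give them a stated place in the sequence. Keep reporting all intervals whatever the outcome. It would also help for 14.4 to say whether the 5% is one-sided or two-sided.

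An equally valid alternative is to state that acuity non-inferiority is claimed only if all three distances pass. This suits a single overall statement about the lens and avoids placing near vision last in a presbyopia study.

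The cost is a few sentences, with no change to sample size, data collection or intervals. Under the fixed sequence a later distance cannot be claimed if an earlier one fails; under the alternative, any one failure blocks the claim. For equal lenses and an assumed paired SD of 0.06 to 0.10 logMAR, the third test keeps about 84% to 100% power, conditional on the primary being met.

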14.5. Primary Analysis

Primary efficacy analysis:

Overall quality of vision scores will be analyzed using a linear mixed model adjusting for baseline values as fixed covariates. The model will include the experimental design factors: sequence of lens wear, period, lens type, time point and interaction between lens and time point as fixed effects. The covariance between residual errors from the same subject across lens wearing periods/time point will be selected based on the finite-sample corrected Akaike's Information Criterion.⁶ Covariance structures considered may include: Homogenous compound symmetry (CS) and Unstructured covariance structure (UN). The structure that returns the lowest Akaike Information Criteria Corrected (AICC) will be selected as the structure that best fit the data.

Comparisons between the Test lens and Control lens at 2-week follow-up will be carried out using 95% confidence intervals constructed of least-square means (LSM) differences (Test minus Control) from the linear mixed model. The non-inferiority of the Test lens relative to the Control will be concluded if the lower confidence limit of LSM difference is above the non-inferiority margin -5. The superiority will be established if the lower confidence limit is above 0.

In all models, the Kenward and Roger method⁷ will be used for the calculation of the denominator of degrees of freedom.

14.6. Secondary Analysis

Secondary efficacy analysis:

Binocular, high luminance, high contrast visual performance on logMAR scale will be analyzed using a linear mixed model to test for the difference between the study lens systems. Each model will include the experimental design factors: sequence of lens wear, lens wearing period, lens type, distance and the interaction between lens type and distance as fixed effects. Other baseline characteristics known of importance such as age, gender, and/or add power will be included as fixed covariates when appropriate. Site and subject nested in site will be included as random effects when appropriate. The covariance between residual errors from the same subject at the same distance across lens wearing periods will be selected based on the finite-sample corrected Akaike's Information Criterion.⁶ Covariance structures considered may include: Homogenous compound symmetry (CS) and Unstructured covariance structure (UN). The structure that returns the lowest Akaike Information Criteria Corrected (AICC) will be selected as the structure that best fit the data.

Comparisons between the Test lens and Control lens will be carried out using 95% confidence intervals constructed of least-square means (LSM) differences (Test minus Control) from the linear mixed models. The non-inferiority of the Test lens relative to the Control will be concluded if the upper confidence limit of LSM difference is below the non-inferiority margin 0.05 logMAR. The superiority will be established if the upper confidence limit is below 0.

14.7. Other Exploratory Analyses

Not Applicable

14.8. Interim Analysis

Not Applicable.

14.9. Procedure for Handling Missing Data and Drop-Outs

Missing or spurious values will not be imputed. The count of missing values will be included in the summary tables and listings.

Subject dropout is expected to be one of the main reasons of missing data in this clinical trial. Past clinical trials don't provide the evidence that subject dropout is systematic or not-at-random. To evaluate the impact of missing data, sensitivity analysis will be conducted using multiple imputation methods if the proportion of subject dropout is greater than the 15%. The SAS/STAT procedures PROC MI and PROC MIANALYZE will be utilized with a parametric regression method used to make at least 5 imputations.

14.10. Procedure for Reporting Deviations from Statistical Plan

The analysis will be conducted according to that specified in above sections. There are no known reasons for which it is planned to deviate from these analysis methods. If for any reason a change is made, the change will be documented in the study report along with a justification for the change.

15. DATA HANDLING AND RECORD KEEPING/ARCHIVING

15.1. Electronic Case Report Form/Data Collection

The data for this study will be captured on electronic case report forms (eCRFs) using an EDC system (Bioclinica). An authorized data originator will enter study data into the eCRFs using the EDC system. Data collected on equipment that is not captured in EDC will be formatted to the specification of the JJV database manager and sent to JJV for analysis.

External Date Sources for this study include:

Not Applicable

The clinical data will be recorded on dedicated eCRFs specifically designed to match the study procedures for each visit. Once completed, the eCRFs will be reviewed for accuracy

and completeness and signed by the Investigator. The sponsor or sponsor's representatives will be authorized to gain access to the subject recordation for the purposes of monitoring and auditing the study.

Edit checks, electronic queries, and audit trails are built into the system to ensure accurate and complete data collection. Data will be transmitted from the clinical site to a secure central database as forms are completed or updated, ensuring information accuracy, security, and confidentiality. After the final database lock, the Investigator will be provided with Individual Patient Profiles (IPP) including the full audit trail on electronic media in PDF format for all of the study data. The IPP must be retained in the study files as a certified copy of the source data for the study.

The content and structure of the eCRFs are compliant with ISO14155:2011.¹

15.2. Subject Record

At a minimum, subject record should be available for the following:

- subject identification
- eligibility
- study identification
- study discussion
- provision of and date of informed consent
- visit dates
- results of safety and efficacy parameters as required by the protocol
- a record of all adverse events
- follow-up of adverse events
- medical history and concomitant medication
- test article receipt/dispensing/return records
- date of study completion
- reason for early discontinuation of test article or withdrawal from the study, if applicable

The subject record is the eCRF or an external record. The author of an entry in the subject record must be identifiable. The first point of entry is considered to be the source record.

Adverse event notes must be reviewed and initialed by the Investigator.

16. DATA MANAGEMENT

16.1. Access to Source Data/Document

The Investigator/Institution will permit trial-related monitoring, audits, IEC/IRB review and regulatory inspection(s) by providing direct access to source data/documents. Should the clinical site be contacted for an audit by an IEC/IRB or regulatory authority, JJV must be contacted and notified in writing within 24 hours.

16.2. Confidentiality of Information

Information concerning the investigational product and patent application processes, scientific data or other pertinent information is confidential and remains the property of JJV. The Investigator may use this information for the purposes of the study only. It is understood by the Investigator that JJV will use information developed in this clinical study in connection with the development of the investigational product and therefore may disclose it as required to other clinical investigators and to regulatory agencies. In order to allow the use of the information derived from this clinical study, the Investigator understands that he/she has an obligation to provide complete test results and all data developed during this study to the Sponsor.

16.3. Data Quality Assurance

Steps will be taken to ensure the accuracy and reliability of data, include the selection of qualified investigators and appropriate clinical sites and review of protocol procedures with the Principal Investigator. The Principal Investigator, in turn, must ensure that all Sub-Investigators and clinical site personnel are familiar with the protocol and all study-specific procedures and have appropriate knowledge of the study article.

Training on case report form completion will be provided to clinical site personnel before the start of the study. The Sponsor will review case report forms for accuracy and completeness remotely during the conduct of the study, during monitoring visits, and after transmission to data management. Any data discrepancies will be resolved with the Investigator or designee, as appropriate.

Quality Assurance representatives from JJV may visit clinical sites to review data produced during the study and to assess compliance with applicable regulations pertaining to the conduct of clinical trials. The clinical sites will provide direct access to study-related source data/documents and reports for the purpose of monitoring and auditing by JJV and for inspection by local and regulatory authorities.

17. MONITORING

The study monitors will maintain close contact with the Principal Investigator and the Investigator's designated clinical site personnel. The monitor's responsibilities will include:

- Ensuring that the investigation is being conducted according to the protocol, any subsequent amendments, and regulatory requirements are maintained
- Ensuring the rights and wellbeing of subjects are protected
- Ensuring adequate resources, including facilities, laboratories, equipment, and qualified clinical site personnel
- Ensuring that protocol deviations are documented with corrective action plans, as applicable
- Ensuring that the clinical site has sufficient test article and supplies
- Clarifying questions regarding the study
- Resolving study issues or problems that may arise

- Reviewing of study records and source documentation verification in accordance with the monitoring plan

